## Participants

We will recruit up to 196 participants (98 male and 98 female adult CC smokers) from the state of Texas and/or Houston metropolitan areas. Inclusion/exclusion criteria are described in **Table 1**. Note: For the purpose of eligibility requirements and ongoing smoking status, "cigarettes" will also include the tobacco product that is commonly known as "little cigars". Little cigars are machine-manufactured and sold in packs similar to cigarettes. They are often smoked by individuals of limited means because they are cheaper than conventional cigarettes.

COVID-19 adaptation: While this study is being conducted virtually, we will expand participant recruitment to the state of Texas.

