**Phases 2 & 3: SREC-NIC and SREC-PLA use (weeks 3-4, 5-6).** During Phases 2 & 3, participants will be provided with SREC-NIC or SREC-PLA, in a counter-balanced fashion (i.e., half will receive SREC-NIC during phase 2 and SREC-PLA during phase 3). The subjects will be randomized on a 1:1 ratio and will be assigned to their randomization group through the protocol specific TRTP database. 50% (70 subjects) will receive the Active study product first and the placebo second and 50% will receive the Placebo study product first and the active study product second. During the randomization process, participants will be stratified by gender for order of exposure to SREC-PLA and SREC-NIC. At the beginning of each phase, each participant will receive 2 SREC devices with non-removable rechargeable batteries (3.3 v, 1000 mAh battery), 1 USB recharger, a 2-week supply of sealed SREC tanks (14 pods; containing either nicotine or placebo e-liquid), a user manual, and a carrying pouch. The SRECS are produced by NJOY LLC (Glenns Ferry, ID) under NIDA contract, and are available in two nicotine doses, 5% (~59 mg/ml nicotine) and 0% (0 mg/mL nicotine; placebo), a single flavor (nicotine), and in sealed disposable pods that deliver <350 puffs/pod . Participants will be instructed to use the SREC during Phases 2 and 3 whenever they get the urge to smoke, but will not be penalized for using their UB CCs or other nicotine products (including other ECs), as product use is a dependent measure in this study. The use of UB CCs and the study products will be documented daily by the participant in Qualtrics as part of the EMA.

At the beginning Phase 2, participants will receive training in how to use the SREC product. They may be shown a brief video demonstrating its use followed by a hands-on training which will include assembly (battery and tank), turning the SREC on and off, puffing, and recharging the battery. The training session will last 30 minutes and will include a minimum of three bouts of 10 puffs each in which the user will be encouraged to vary puff topography to maximize desired sensory qualities of product use. This procedure is currently being used by us in our active EC grant (R01DA042526), and has been found to result in users achieving

**Figure 1.** Timeline of study procedures.

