### Statistical Approach & Expected Outcomes

**General Data Analytic Strategy.** To analyze our aims, we will use a crossover design model with  $n = 140$  subjects (assuming 15% attrition of  $n=164$ ) and  $k = 3$  periods. In this design,  $t_0$  and  $t_1$  will be the two SREC types, with  $t_0$  for SREC-PLA and  $t_1$  for SREC-NIC. We will use the following model for  $y$  (e.g., CPD):  $y_{ij} = b_1 + b_{2t(i,j),t(l,j-1)} + e_{ij}$ , where  $b_1$  is the effect of subject  $i$ , and  $b_2$  is the effect of treatment  $t_{10}$  when preceded by treatment  $t_{10}$ .  $T(i,j)$  is the treatment assigned to subject  $i$  in period  $j$ , for  $1 \leq i \leq n$  and  $1 \leq j \leq k$ . The residual errors  $e_{ij}$  are assumed to be independent and identically distributed with expectation 0 and variance  $\sigma^2$ . In this design, each subject will act as its own control reducing the influence of confounding, reducing variance and improving accuracy and sensitivity for the estimated effect of interest. In the interaction models (Aim 2), gender will be entered in the equation and interacted with  $b_{2t(i,j),t(l,j-1)}$  to estimate gender by treatment interaction effects on all outcomes. Period and carryover effects will be evaluated by testing equivalence of effects across time (e.g., CPD collected using TLFB). We will utilize a mixed model approach for estimation using the "glmer" function of the "lme4" R package. Missingness will be treated as missing-at-random within maximum likelihood estimation and we will utilize not-missing-at-random approaches (e.g., pattern mixture model) if non-ignorable missingness is suspected. Given the large number of outcomes, the analyses will address issues of multiplicity by applying the False Discovery Rate.

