### Power and Sample Size

Our power analyses were conducted using a sample size of n=140 total participants. However, we will recruit and randomize n=164 because we expect a 15% drop-out rate by Week 6, based on the attrition rate of our existing EC product switching protocol (2015-0638). To demonstrate that we have adequate statistical power to detect likely effect sizes with n=140, we conducted power analyses for Aim 1 (i.e., the main effect of SREC type) and Aim 2 (i.e., the interaction between gender and SREC type) on our primary outcome measure, CPD collected from TLFB. However, in our attempt to estimate likely CPD effect size differences by gender as a function of SREC exposure (Aim 2), we were limited because there were no published studies that reported gender differences in CC and EC product use among CC smokers who were switched to nicotine and/or placebo ECs. Instead, to estimate the effect size of switching from CCs to ECs on CPD, we used a study  that examined the impact of switching to 18 mg ECs over 2 weeks that found that participants reduced their CPD by 96.3% (16.2 to 0.6 CPD). This allowed us to estimate the impact of switching to an EC with nicotine amounts similar to that of the SREC. To estimate the impact of product nicotine dose and gender on CPD, we used a study  that examined the impact of switching CC smokers to either VLNC (0.05 to 0.09 mg nicotine yield) CCs alone or combined VLNC cigarettes and NRT (21 mg patch). While this study did not include ECs, it allowed for the examination of the impact of nicotine on CPD, by gender, and found that men in the nicotine group (VLNC+NRT) smoked less VLNC CCs at week 2 than women .

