that use of a closed-tank ECIG device among adult smokers results in relatively few adverse events. In this protocol (2015-0638; R01DA042526), which is ongoing, we are testing the strategy of simultaneously providing a smoker uninterested in quitting with both VLNCs as well as an ENDS product to determine if they will compensate for the reduction in nicotine from the VLNC's with the ENDS product. This is critical to the regulatory strategy aimed at determining nicotine levels in future ENDS product, because we may wish to maximize compensation in order to move people away from combustibles and increase the likelihood of cessation. Thus far, we have exposed 176 adult smokers to NIDA's VLNC combustible cigarette for up to 9 weeks and to commercially available closed-tank electronic cigarettes for up to 6 weeks (the same product being used in many other studies across the country). In terms of adverse events, similar proportions of participants have reported adverse events during the exclusive cigarette phases (18.0%) than during the phase where they are encouraged to use electronic cigarettes instead of smoking (15.3%). The most frequently reported adverse events during the electronic cigarette phases included depressive symptoms (n=4), sore throat (n=3), diarrhea (n=2), toothache (n=2), and vomiting (n=2). For the exclusive cigarettes phases, the most common adverse events included cough (n=6), irritability (n=5), headache (n=4), back pain (n=2), diarrhea (n=2), limb edema (n=2), insect bite (n=2), nausea (n=2), panic attack (n=2), and urinary tract infection (n=2). No severe adverse event was reported during the electronic cigarette phases, but one was reported during the exclusive cigarette phases, brachycardia (n=1). None of these were determined to be of probable or definitive relation to the study product. No serious respiratory symptoms have been reported. Our retention rate through the end of study has been 77%. The preliminary findings suggest that closed-tank electronic cigarettes are not associated with more adverse events than smoking combustible cigarettes.

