**Consideration of Relevant Biological Variables.** We will recruit an equal number of male and female adult daily smokers for this study because gender differences form the main focus of this proposal. While biological sex is the primary independent variable, we will also account for other relevant biological variables, such as age, by including them as covariates of interest in our statistical models. We are using multilevel models to partially pool the estimate from each covariate toward the overall mean of all estimates. This is a natural away to account for multiple comparisons without sacrificing power (which we do in the case of Bonferroni correction). Each effect is shrunk toward the overall estimate. The higher the uncertainty of a specific effect the more it shrinks toward the overall estimate.

**Timetable.** After a 3-month study setup, we expect to enroll between months 6 and 20, at a rate of 10 subjects per month (see **Table 3**). The final participant session will be during month 22, and data analysis and initial manuscript drafting will occur by month 24.

**Future directions.** At the project's conclusion, we will be able to provide scientific information on gender differences in terms of the extent to which the NIDA SREC is used and accepted by adult CC smokers, which would indicate whether it could serve as a good model of future EC research. We will also identify factors that moderate or mediate the effects of switching to nicotine and placebo SRECs from CCs. Our next steps will be to submit proposals

hormonal contraception. However, we will capture self-report of both factors and use them as moderators (hormonal contraceptive use) and mediators (menstrual phase) as part of the exploratory aim.

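### The Aim 1 model leaves out the gender by SREC-type term, although order is randomised within gender and men and women are recruited equally; the cost is small but easily avoided

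*Combined protocol and SAP*

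**What the plan says.** - **Randomisation** (Procedures, Phases 2 & 3): "The subjects will be randomized on a 1:1 ratio" to the two orders, and "participants will be stratified by gender for order of exposure to SREC-PLA and SREC-NIC".
- **Recruitment:** the Participants section sets up to 98 men and 98 women. The paragraph on relevant biological variables repeats it: "We will recruit an equal number of male and female adult daily smokers for this study".
- **Model** (General Data Analytic Strategy): a subject effect plus a treatment effect indexed by the preceding treatment. Gender is added for Aim 2: "In the interaction models (Aim 2), gender will be entered in the equation and interacted with" that treatment effect. No gender term is written for Aim 1, and nothing says how men and women are averaged in the overall SREC effect.
- **Hypothesis** (Aim 2): men are expected to respond more than women to SREC-NIC relative to SREC-PLA, which is a gender by SREC-type interaction. CPD is the primary outcome for both aims.
- **Dropout** (Power and Sample Size): "we will recruit and randomize n=164 because we expect a 15% drop-out rate by Week 6". It is not broken down by gender. Missing data are treated as missing at random within maximum likelihood.

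**The concern.** The design fixes a 50:50 gender mix and balances order within it. The Aim 1 analysis uses neither fact. Two things could follow.

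1. If the SREC effect differs by gender, that difference sits in the Aim 1 residual and enlarges the reported standard error.
2. If men and women also drop out at different rates, the Aim 1 estimate is weighted towards whichever gender supplies more data. Gender-related dropout is then missing at random only given a term that the Aim 1 model lacks and the Aim 2 model has. The same assumption would be applied under two different models of one primary outcome.

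At stake are a little power and a small movement of the Aim 1 estimate away from the population that was randomised.

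**Working it through.** **Inputs from the plan.** 140 analysed of 164 randomised; 80% power for 1.75 CPD (Aim 1) and for 3.5 CPD (Aim 2 interaction); 15% dropout overall.

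**Assumptions not in the plan.** Two-sided alpha 0.05; 70 men and 70 women analysed; dropout rates by gender; between-person SD of CPD. The preceding-treatment index is ignored, so the SREC effect is one within-person difference averaged over the two orders.

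**1. The plan's own figures.** Neither the SD of CPD nor alpha is stated, so the simulated power cannot be reproduced independently. The two figures can be checked against each other, with 1.960 + 0.842 = 2.802:
- Aim 1: SD of the within-person difference = 1.75 x sqrt(140) / 2.802 = 7.39.
- Aim 2: the standard error is SD x sqrt(1/70 + 1/70) = 2 x SD / sqrt(140), so SD = 3.5 x sqrt(140) / (2 x 2.802) = 7.39.

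They agree. I take 7.39 as the within-gender SD, with variance 54.6. The Aim 1 standard error is then 7.39 / sqrt(140) = 0.6246.

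**2. Gender main effect alone.** Gender is constant within a person, so it drops out of the NIC minus PLA difference. With complete data the standard error is 0.6246 with or without it. With 24 of 164 leaving after Phase 2, a between-person SD of 4 to 8 and a gender gap of up to 6 CPD (all assumed), the gain is at most about 0.2%.

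**3. Omitted interaction.** With equal numbers, an interaction of size d adds (d/2)^2 to the variance of the differences. Power is Phi(1.75/SE - 1.96).

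| d (CPD) | Variance with term omitted | SE omitted | SE fitted | Reduction from fitting | Power, omitted |
|---|---|---|---|---|---|
| 0 | 54.6 | 0.6246 | 0.6246 | 0% | 80.0% |
| 1 | 54.6 + 0.25 | 0.6261 | 0.6246 | 0.2% | 79.8% |
| 1.75 | 54.6 + 0.77 | 0.6290 | 0.6246 | 0.7% | 79.5% |
| 3.5 | 54.6 + 3.06 | 0.6419 | 0.6246 | 2.7% | 77.8% |

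If 7.39 is read instead as the total SD, power at d = 3.5 goes from 80% with the term omitted to about 82% with it fitted. That is about two points either way. At alpha 0.025 or 0.10 the implied SD is 6.72 or 8.33 and the conclusion is the same.

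**4. Weighting.** Using people with both SREC phases, the male share is w = (1 - dropout in men) / [(1 - dropout in men) + (1 - dropout in women)], and the shift is (w - 0.5) x d.
- 10% v 20%: w = 0.90/1.70 = 0.529; shift = 0.029 x 3.5 = 0.10 CPD.
- 5% v 25%: w = 0.95/1.70 = 0.559; shift = 0.059 x 3.5 = 0.21 CPD.
- Equal dropout or d = 0: no shift.

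These depend on dropout fractions only, so the choice of recruitment total does not matter. They are upper values, because a likelihood fit also uses the first SREC phase of people who leave after it. In a three-phase random-intercept fit with dropout after Phase 2 (residual SD 7.39/sqrt(2) = 5.23), the shifts fall to about 0.06 and 0.13 CPD.

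Against the 1.75 CPD detectable effect, the full range of 0.06 to 0.21 CPD is 3% to 12%.

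**5. Cost of equal weighting.** With m men and f women completing, the standard error is 7.39 x sqrt(0.25/m + 0.25/f), against 0.6246 pooled:
- 74/66: 0.6257, 0.2% larger.
- 78/62: 0.6288, 0.7% larger.
- 80/60: 0.6311, 1.0% larger.

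**The case against.** **No stated target.** The plan never defines the Aim 1 effect as an equal-weighted average, and equal recruitment is justified by the interest in gender differences, which serves Aim 2. An average over whoever supplies data is a legitimate quantity. This stands as far as it goes, but the randomised population is 50:50 by design, so an estimate that moves with dropout no longer describes that population.

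**3.5 CPD is a detectable difference, not an expected one.** This stands. The plan says that reliable interaction effect sizes are lacking. At 1.75 CPD or less the change in standard error is 0.7% or less.

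**Already available.** The Aim 2 model contains the needed terms, and the biological-variables paragraph calls sex the primary independent variable. That is largely true, but the paragraph does not put gender by SREC type into Aim 1. With 0/1 coding, the SREC coefficient in the Aim 2 model is the effect in the reference gender, not the average, and no coding is given.

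**Stronger readings.** A reader might infer that ignoring a stratification factor costs Aim 1 real precision, as it can in a parallel-group trial. It does not here, because the contrast is within person. Even with an interaction, the true sampling spread of the estimate hardly changes; it is the reported standard error that is too large. A reader might also infer serious bias from a split such as 80 men and 60 women completing, which shifts completer weighting by (80/140 - 0.5) x 3.5 = 0.25 CPD. From 82 of each gender, that needs about 2% dropout in men and 27% in women, and nothing in the plan supports such a gap.

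**Conclusion.** The point holds as a minor improvement. The Aim 1 model as written omits an interaction that the trial hypothesises and that its stratified, equal-gender design makes easy to include. The consequence is at most a reported standard error that fitting the term would lower by 2.7%, worth about two points of power. If dropout differs by gender, there is also a shift of roughly 0.06 to 0.21 CPD. These upper sizes require a 3.5 CPD interaction, and the shift also requires dropout gaps that are assumed here. Without an interaction both effects vanish; with equal dropout the shift vanishes. The results rest on two-sided alpha 0.05 and an SD inferred from the plan's power statements. The validity of Aim 1 is not in question.

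**What to change.** In the General Data Analytic Strategy, state that Aims 1 and 2 come from one model with gender coded +/-0.5 and a gender by SREC-type term. Report the SREC-type coefficient as the Aim 1 effect, that is, the equal-weighted average of men and women, and the interaction coefficient as the Aim 2 effect.

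The cost is a line of text and one or two degrees of freedom. If completers are unbalanced and there is no interaction, the standard error is about 0.2% to 1% larger than under pooling. No change to design, sample size or data collection is needed.

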**Inclusion Criteria:**

- Aged 21 years or older
- Reports being a daily or non-daily smoker (any self-reported smoking in the past 30 days)
- Have an address where he/she can receive mail
- Able to follow verbal and written instructions in English and complete all aspects of the study as determined by PI
- Willing to have urine biospecimen samples taken, either in-home and returning them by mail, or in-person at an approved collection site.
- Willing to use tobacco-flavored study electronic cigarettes
- Agrees to comply with all MD Anderson institutional policies related to COVID-19 screening prior to any in-person research visit.
- The individual agrees to not engage in study procedures or interactions with study personnel while operating a vehicle.

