Following the medical team clearance to proceed to Visit 1, a study supply kit will be sent containing the urine specimen collection supplies and other study materials.

**Study Supply Kit: Baseline Screening Visit.** The following items are included in the initial study supply kit:

- Written instructions
- Urine collection kit
- Reloadable gift card (e.g., Bank of America or another approved institutional option)
- Return address label, postage-paid, and box for shipment
- Biospecimen bag, absorbant test tube sleeves

The study specific supplies will be shipped to eligible participants and tracked through eShipGlobal or a comparable system within two business days of completion of the Baseline

Screening Visit. Mailing time may be adjusted due to carrier delays, holidays, or any other factor impacting delivery time. Written instructions will be provided and the research team will be available to guide participants through the sample collection process as needed. The participant must complete and return the required samples to the MD Anderson research team prior to Visit 1, or Visit 1 may be rescheduled.

[figure not shown]
**Phase 1: UB Baseline (weeks 1-2).** During this phase, participants will be instructed to smoke their usual brand *ad libitum*. Measures specific to this phase will be captured at a virtual or in-person visit at the end of week 2. Daily smartphone EMA assessments, as described below, will occur throughout Phase 1. Refer to **Figure 1** for a timeline of study procedures.

COVID-19 adaptation: No adaptations needed.

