Because of the absence of reliable effect sizes of the interaction effect under study in the literature, we estimated power for a series of effect sizes for both the direct and indirect effect. To perform the power analysis we first generated the matrix for our crossover design using the "samplingDataCRT" R package to sample data that reflects our prospective analysis. After generating the sample data, we calculated power for both the main effect of SREC type on CPD (Aim 1) and the SREC type by gender interaction (Aim 2) using three steps: 1) generate new CPD values from the crossover model defined above, 2) refit the model to the simulated data, and 3) evaluate the true positive success rate using the "simr" package . We ran 1000 simulations for each estimation for a series of effect sizes and for both the main effects and interaction models. **Figure 2** presents the power curves of these analyses. For the gender by SREC type interaction (Aim 2), **Figure 2** indicates that we have 80% power to detect a difference of 3.5 CPD or larger between the genders during SREC-NIC. For the SREC type main effect (Aim 1), **Figure 2** (inset) indicates that we have 80% power to detect a difference of 1.75 CPD or larger between SREC-NIC and SREC-PLA. The minimal detectable effect size is larger for the interaction effect compared to the main effect due to the increased power required to detect subgroup effects in randomized trials . Since the main modeling framework is linear, the interaction effect under study has an additive interpretation, such that the combined effects of SREC-NIC and being male contributes more to CPD reduction than the individual effects of the two factors. Additive interaction effects are more relevant for public health decision making and require a lower sample size than multiplicative interaction effects . In conclusion, our proposed sample size of 140 provide enough power to detect a CPD change of 1.75 for the main effect of SREC type and a CPD reduction of 3.5 for the proposed interaction effect, which we believe will be adequate to detect the likely differences we would observe.

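### The nicotine-placebo standard error rests on a variance assumption about the non-randomised usual-brand phase, and the promised carryover check is too weak to reassure

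*Combined protocol and SAP*

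**What the plan says.** All references are to the Combined protocol and SAP.

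- **Model.** General Data Analytic Strategy gives CPD a subject effect and a treatment effect that depends on the preceding treatment, over k = 3 periods in 140 subjects. The residuals "are assumed to be independent and identically distributed with expectation 0 and variance" σ². The equation is damaged in the available text, so I read its structure from the verbal description. Symbols are defined only for the two SREC types. That usual brand is the third period is inferred from k = 3 and the three phases.
- **Order effects.** "Period and carryover effects will be evaluated by testing equivalence of effects across time (e.g., CPD collected using TLFB". No contrast or margin is given.
- **Design.** Under Procedures, Phase 1 is the same for everyone: "During this phase, participants will be instructed to smoke their usual brand". Randomisation decides only the order of NIC and PLA in Phases 2 and 3 (weeks 3-4 and 5-6). No washout is stated.
- **Power.** The simulations "generate new CPD values from the crossover model defined above", and the result is that "we have 80% power to detect a difference of 1.75 CPD or larger between SREC-NIC and SREC-PLA", with 3.5 CPD for the gender interaction. The planning study is one in which "participants reduced their CPD by 96.3% (16.2 to 0.6 CPD". Table 1 admits a wide range of smokers: "Reports being a daily or non-daily smoker (any self-reported smoking in the past 30 days".
- **CPD source.** Assessment of product use takes primary CPD from the daily smartphone diary, with TLFB filling gaps. Power and Sample Size bases power "on our primary outcome measure, CPD collected from TLFB".

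**The concern.** NIC minus PLA is a comparison of Phase 2 with Phase 3 within a person. A single residual variance over three phases also draws on the two differences that involve usual brand. If people differ in how far they fall from usual brand, those differences are more variable than the one that matters, and the model carries that extra variation into the error of the randomised contrast. The Aim 1 and Aim 2 tests both use this error, and power was simulated from the same model.

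The SREC phases are also consecutive, so readers will lean on the sentence about period and carryover. It matters whether that check can distinguish the two, and whether a non-significant result would rule out carryover large enough to change the answer.

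**Working it through.** **Inputs.** n = 140, 70 per sequence; 1.75 and 3.5 CPD at 80% power (Power and Sample Size). Assumed, because the documents are silent: two-sided alpha 0.05 and ICC 0 to 0.7, where ICC is between-person variance over between-person plus residual variance.

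**1. The plan's own figure.** 1.75 cannot be derived without an SD. Back-solving on the sequence-averaged contrast: SE = 1.75/2.8016 = 0.625. Since Var = 2σ²/n, σ = 0.625 × √70 = 5.23 and σ² = 27.3. The two stated figures agree with each other: with equal gender groups the interaction SE is twice the main-effect SE, and 3.5/1.75 = 2.0.

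**2. Residual.** Let Vjk be the variance of the difference between phases j and k.

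model SE / true SE = √{[(V12 + V13 + V23)/3] / V23}

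Let the individual usual-brand drop, shared by both SREC phases, have SD d. Then V23 = 2σ² and V12 = V13 = 2σ² + d², so the ratio is √(1 + d²/(3σ²)). Power at 1.75 is Φ(2.80 − 1.96 × ratio).

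| d (assumed, CPD) | SE ratio | Power at 1.75 |
|---|---|---|
| 3 | √(1 + 9/81.9) = 1.05 | 77% |
| 5 | √(1 + 25/81.9) = 1.14 | 71% |
| 7 | √(1 + 49/81.9) = 1.26 | 63% |

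A simulation of 20,000 runs gave 77%, 71% and 62%, against 80% for a model of the two randomised phases. Aim 2 at 3.5 CPD has the same signal-to-error ratio (3.5/1.249 = 2.80), so these powers apply to it too.

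**3. What the check can identify.** Let τ be NIC minus PLA, λ the carryover common to both products, δ the carryover from NIC minus that from PLA, and π2, π3 the period effects.

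| Sequence | Phase 1 | Phase 2 | Phase 3 |
|---|---|---|---|
| NIC first | μ | μ + π2 + τ/2 | μ + π3 − τ/2 + λ + δ/2 |
| PLA first | μ | μ + π2 − τ/2 | μ + π3 + τ/2 + λ − δ/2 |

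π3 and λ appear only as a sum: six parameters, rank 5. Adding a period term to the plan's five treatment-given-predecessor cells leaves the rank at 5. NIC minus PLA is τ in Phase 2 and τ − δ in Phase 3. The averaged contrast is therefore τ − δ/2, free of λ but biased by half of δ. The between-phase difference estimates δ, and a treatment-by-period interaction would look identical.

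**4. Precision of the check.** With usual brand as baseline, SE(δ) = √[8(1 + 2·ICC)σ²/n]. For the Phase 2-only contrast, SE = √[4(1 + ICC)σ²/n]. Detectable values are 2.80 × SE.

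| ICC | SE(δ) | Detectable δ | Bias at that δ | Power if δ = 1.75 | Phase 2-only detectable |
|---|---|---|---|---|---|
| 0 | 1.249 | 3.50 | 1.75 | 29% | 2.47 |
| 0.3 | 1.580 | 4.43 | 2.21 | 20% | 2.82 |
| 0.5 | 1.767 | 4.95 | 2.47 | 17% | 3.03 |
| 0.7 | 1.935 | 5.42 | 2.71 | 15% | 3.23 |

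I stop at ICC 0.7, where the between-person SD is 5.23 × √(0.7/0.3) = 8.0 CPD. At 0.9 it would be 15.7, about the whole 16.2 CPD baseline mean of the planning study.

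**The case against.** **No size from the documents.** With no SD, ICC or alpha stated, 5.23 is back-solved and d is assumed. This stands: the powers in step 2 are illustrations. It also cuts another way. If the simulated residual already contained the variation in drops, 1.75 is conservative. The two-phase model would then detect 1.75 × √((27.3 − 3.0)/27.3) = 1.65 CPD at d = 3 and 1.75 × √((27.3 − 16.3)/27.3) = 1.11 CPD at d = 7. Sensitivity would be given up, but the stated power would hold.

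**The planning study does not fix d.** A reader might apply the 96.3% fall proportionally and read off a drop SD. A mean near 0.6 CPD does not fit with a residual SD of 5.23, because CPD cannot be negative. The plan itself expects incomplete switching: its literature review foresees dual use, and Potential Problems allows for low SREC use. The fall towards zero and the broad eligibility give reason to expect unequal falls, but no number.

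**Carryover is already modelled.** True: treatment is indexed by its predecessor, so the Phase 2-only contrast and the between-phase difference are contrasts of the plan's own cells. The SREC-type main effect is named as the Aim 1 target. What is missing is how it is formed from those cells and which contrast the check uses.

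**Common carryover is harmless.** A reader might infer that its aliasing with period biases NIC minus PLA. It does not (step 3). It limits only what the check can show.

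**Weak carryover tests are generic to two-sequence crossovers.** Also true, and no analysis of this design cures it. That is a reason to report an interval and state the limit, not to imply that equivalence can be shown.

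**Conclusion.** The point holds as an avoidable assumption and an over-promising check.

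- **Residual.** The NIC-PLA standard error depends on an untested equality of variances involving a phase that was not randomised. Size is unknown. The available evidence points mainly to an error that is too large: 5% to 26% under the assumed drop SDs of 3 to 7 CPD.
- **False positives.** A reader might infer an inflated type I error. That is possible in principle, if usual-brand residual variance were lower than in the SREC phases, but no section supports it, so I do not claim it.
- **Check.** Inseparability of common carryover and period follows from the design and needs no numerical assumption. The imprecision for differential carryover rests on the back-solved SD and ICC 0 to 0.7. A differential carryover equal to the full 1.75 CPD would bias the contrast by 0.875 CPD, yet be flagged only 15% to 29% of the time.
- **CPD source.** The diary-TLFB conflict is a plain contradiction in the text. TLFB is only an example in the sentence on order effects, but the power section calls it primary.

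**What to change.** 1. Estimate the Aim 1 effect and its standard error from Phases 2 and 3: CPD on period, SREC type and a random subject effect. Aim 2 adds gender and gender by SREC type. Alternatively keep three phases with an unstructured phase covariance.
2. Replace the equivalence sentence with the between-phase difference in the NIC-PLA contrast and its 95% CI, labelled *differential carryover or treatment-by-period*. State that common carryover and period cannot be separated, and that the primary estimate is biased by half of any differential carryover. Report the Phase 2-only contrast, adjusted for usual brand, as a sensitivity analysis.
3. Reconcile Assessment of product use with Power and Sample Size on the primary CPD source, and use that source for both the primary analysis and the check.

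**Cost.** Wording and code, with no new data. Period takes one degree of freedom, and there is slightly more analysis. Under the two-phase model, change from usual brand, including the hypothesised gender difference in cigarette reduction, moves to a separate uncontrolled model. If the iid assumption is true, the standard error is unchanged at 0.625. The fix does not remove carryover bias. The Phase 2-only contrast avoids it but is less precise, so it is proposed as sensitivity and not as primary.
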